##### Onset Date

Partial AE onset dates will be imputed as follows:

- If the onset date of an adverse event is missing day only, it will be set to:
  - First day of the month that the AE occurred, if month/year of the onset of AE is different than the month/year of the treatment phase start date
  - The day of treatment phase start date, if the month/year of the onset of AE is the same as month/year of the treatment phase start date and month/year of the AE resolution date is different.
  - The day of treatment phase start date or day of AE resolution date, whichever is earliest, if month/year of the onset of AE and month/year of the treatment phase start date and month/year of the AE resolution date are same
- If the onset date of an adverse event is missing both day and month, it will be set to the earliest of:
  - January 1 of the year of onset, as long as this date is on or after the treatment phase start date.
  - One day after the treatment start date, if this date is the same year that the AE occurred
  - Last day of the year if the year of the AE onset is prior to the year of the treatment phase start date
  - The AE resolution date.
- Completely missing onset date of an adverse event will be set to the treatment phase start date.

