8.3. Adverse Events and Serious Adverse Events

Timely, accurate, and complete reporting and analysis of safety information from clinical studies are crucial for the protection of participants, investigators, and the sponsor, and are mandated by regulatory agencies worldwide. The sponsor has established Standard Operating Procedures in conformity with regulatory requirements worldwide to ensure appropriate reporting of safety information; all clinical studies conducted by the sponsor or its affiliates will be conducted in accordance with those procedures.

Adverse events will be reported by the participant (or, when appropriate, by a caregiver, surrogate, or the participant's legally acceptable representative) for the duration of the study.

For further details on AEs and SAEs (Definitions and Classifications; Attribution Definitions; Severity Criteria; Special Reporting Situations; Procedures) as well as product quality complaints (PQCs), refer to Section 10.4, Appendix 4, Adverse Events: Definitions and Procedures for Recording, Evaluating, Follow-up, and Reporting.

8.3.1. Time Period and Frequency for Collecting Adverse Event and Serious Adverse Event Information

All Adverse Events

All AEs and special reporting situations, whether serious or nonserious, will be reported from the time a signed and dated ICF is obtained until 30 days after the last dose of study intervention. Serious adverse events (SAEs), including those spontaneously reported to the investigator within 30 days after the last dose of study intervention, must be reported using the Serious Adverse Event Form. The sponsor will evaluate any safety information that is spontaneously reported by an investigator beyond the time frame specified in the protocol.

Serious Adverse Events

All SAEs occurring during the study must be reported to the appropriate sponsor contact person by study-site personnel within 24 hours of their knowledge of the event. Also, SAEs that occur after 30 days following the last intervention administration and are considered to be related to the study intervention will be collected and reported to the appropriate sponsor contact person.

Information regarding SAEs will be transmitted to the sponsor using the Serious Adverse Event Form, which must be completed and signed by a physician from the study site, and transmitted to the sponsor within 24 hours. The initial and follow-up reports of an SAE should be made according to the safety monitoring plan.

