#### 2.4. Imputation Rules for Missing AE Date/Time of Onset/Resolution

Treatment-emergent adverse events (TEAEs) for the treatment phase are those events with an onset date/time on or after the start of study intervention through the day of last dose plus 30 days is considered to be treatment -emergent.

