### **6.1. Adverse Events**

The verbatim terms used in the CRF by investigators to identify adverse events (AE) will be coded using the Medical Dictionary for Regulatory Activities (MedDRA). Any AE occurring at or after the initial administration of study agent through the day of last dose plus 30 days is considered to be treatment emergent. If the event occurs on the day of the initial administration of study agent, and either event time or time of administration are missing, then the event will be assumed to be treatment emergent. If the event date is recorded as partial or completely missing, then the event will be considered to be treatment emergent unless it is known to be prior to the first administration of study agent based on partial onset date or resolution date. All reported treatment-emergent adverse events will be included in the analysis. For each adverse event, the number and percentage of subjects who experience at least 1 occurrence of the given event will be summarized.

A summary for tables and listings is shown in [Table 7](#):

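### SAP 2.4 and SAP 6.1 give opposite treatment-emergent status to an adverse event in two narrow missing-date situations

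*SAP*

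**What the plan says.** SAP 2.4 opens with its own TEAE definition: events "with an onset date/time on or after the start of study intervention through the day of last dose plus 30 days". Its onset rules then depend on how much of the date is missing.

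- Day missing, onset month different from the treatment start month: "First day of the month that the AE occurred, if month/year of the onset of AE is different".
- Day missing, with onset, treatment start and resolution all in one month: "The day of treatment phase start date or day of AE resolution date, whichever is earliest".
- Day and month missing: the earliest of several candidates, which include "January 1 of the year of onset, as long as this date is on or after the treatment phase start date" and the resolution date.
- Everything missing: "Completely missing onset date of an adverse event will be set to the treatment phase start date".

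SAP 6.1 states the same general window and adds a separate sentence for partial or completely missing dates: "then the event will be considered to be treatment emergent unless it is known to be prior to the first administration of study agent". The evidence it accepts for that exception is the partial onset date or the resolution date. It gives no matching exception for dates after the window.

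Events outside the window do reach the database. Protocol 8.3.1 collects adverse events from consent, and screening runs up to 28 days before first dose (Protocol 5). After treatment, "SAEs that occur after 30 days following the last intervention administration and are considered to be related to the study intervention will be collected". Neither SAP section says which one governs.

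**The concern.** TEAE status decides which events enter most of the tables in SAP Table 7. If two sections of one plan classify the same record differently, the count depends on which one is programmed.

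The completely-missing rule looks like an oversight. The same-month rule and the day-and-month rule in SAP 2.4 both allow an earlier resolution date to take over; this rule does not, so it can produce an onset after the event has ended. In the other direction, the exception in SAP 6.1 covers only events before first dose. A related serious event known to have begun after the window therefore becomes a TEAE merely because its day is unknown; with a full date it would be excluded under both sections.

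**Working it through.** The plan gives no figure on this point, so the check is to apply both rules as written and compare.

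**Rules applied**

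- SAP 2.4: impute the onset, then call the event a TEAE if first dose ≤ imputed onset ≤ last dose + 30 days.
- SAP 6.1: call it a TEAE unless the partial onset or the resolution date shows that it preceded first dose.

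**Case A.** First dose 1 September 2020; onset completely missing; resolved 4 August 2020.

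- SAP 2.4: imputed onset = 1 September 2020, which is 28 days after resolution. It lies in the window, so TEAE.
- SAP 6.1: resolution precedes first dose, so not a TEAE.

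**Case B.** Last dose 29 September 2020; the window ends 29 September + 30 days = 29 October 2020; onset recorded as November 2020, day unknown.

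- SAP 2.4: imputed onset = 1 November 2020, after 29 October, so not a TEAE.
- SAP 6.1: not known to precede first dose, so TEAE.
- With only the year 2021 recorded, SAP 2.4 imputes 1 January 2021 and the same conflict follows.

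**Everywhere else.** Both rules were run over a grid: first-dose dates across a year, treatment durations of 28 to 300 days, onsets from 28 days before first dose to 120 days after last dose, several resolution times, and three kinds of missingness. The counts show only which situations conflict; they are not expected frequencies.

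| Recorded onset | True situation | SAP 2.4 | SAP 6.1 | Combinations |
|---|---|---|---|---|
| All missing | Resolved before first dose | TEAE | not | 4,100 of 4,100 (**A**) |
| All missing | Began before first dose, not resolved by then | TEAE | TEAE | 5,740 |
| All missing | Began after the window | TEAE | TEAE | 29,520 |
| Day missing | Resolved before first dose | not | not | 4,100 of 4,100 |
| Day missing | Began before first dose, not resolved by then | same as 6.1 | same as 2.4 | 2,456 not; 3,284 TEAE |
| Day missing | After window, but first of month still inside it | TEAE | TEAE | 4,884 |
| Day missing | Onset month wholly after window | not | TEAE | 24,636 (**B**) |
| Day and month missing | Resolved before first dose | not | not | 4,100 of 4,100 |
| Day and month missing | Began before first dose, not resolved by then | same as 6.1 | same as 2.4 | 188 not; 5,552 TEAE |
| Day and month missing | After window, imputed date inside it | TEAE | TEAE | 25,668 |
| Day and month missing | Onset year wholly after window | not | TEAE | 3,852 (**B**) |
| Any of the three | Began inside the window | TEAE | TEAE | 57,318 each |

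**Size.** SAP 6.1 counts participants with at least one occurrence. One extra participant moves a row by 1/24 = 4.2 percentage points at the target of about 24 treated, and by 1/25 = 4.0 points with 25. The row moves only if that participant has no other event in it.

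**The case against.** The best defence is that SAP 6.1 governs the tables and should be read as a whole. It decides TEAE status from dates as recorded, sits directly before the table list, and accepts the resolution date as evidence, so case A is excluded. Its first lines end the window at last dose plus 30 days, so the missing-date sentence can be read as a presumption inside that window, which would exclude case B too. This is a sensible reading, but the SAP does not state it. SAP 2.4 also defines TEAEs at the head of its imputation rules, so it does more than assign a date. The missing-date sentence in SAP 6.1 is the specific rule for these records and lists one exception. Even on the generous reading, case A leaves an imputed onset after resolution.

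The defence is right about rarity. Case A needs an event with no day, month or year of onset but a recorded resolution, within a short screening period and after data queries. Case B is confined to related serious events, because nothing else is collected that late. Efficacy and futility rest solely on response rate (SAP 3), and both errors add events rather than hide them.

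A reader might go further in three ways that the documents do not support:

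- *That the sections conflict on missing dates in general.* They conflict only in A and B.
- *That late serious events are especially likely to carry partial dates because follow-up contact is every 6 months.* No document gives a rate of partial dates. Protocol 7.1 adds an end-of-treatment visit within 30 days, participants who stop for safety or tolerability continue imaging (Schedule of Activities, footnote c), and Protocol 8.3.1 requires serious events to be reported within 24 hours of the site learning of them.
- *That any misclassified participant moves any adverse event table by 4.2 points.* That holds only for a row in which the participant has no other event, and only with 24 treated.

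**Conclusion.** The point stands as a narrow wording error. Read literally, SAP 2.4 misclassifies case A and SAP 6.1 misclassifies case B against the SAP's own window. Naming one section as governing is therefore not enough: SAP 2.4 alone leaves A wrong, and SAP 6.1 alone leaves B wrong.

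The effect is small. It is confined to descriptive safety tables and cannot change the primary analysis. It is about 4 percentage points in an affected row, assuming about 24 treated participants. That would be visible in a serious-event or single-term row with few events. How often either case will occur cannot be estimated from the documents beyond saying that it should be rare.

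**What to change.** Make three edits before database lock.

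1. SAP 2.4, completely missing onset: *set to the earlier of the treatment phase start date and the AE resolution date*. With no resolution date, the treatment start date still applies. In the example for A, onset becomes 4 August 2020, so the event is not a TEAE under either section and the impossible date order disappears.
2. SAP 6.1, missing-date sentence: add to the exception *or the partial onset date shows it was after last dose plus 30 days*. In the example for B, November 2020 is then excluded under both sections.
3. State in SAP 6.1 that it classifies using the dates imputed in SAP 2.4.

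The cost is two amended sentences and one new one, with matching programming. No new data are needed, and study conduct does not change.

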##### Resolution Date

Partial AE resolution dates not marked as ongoing will be imputed as follows:

- If the resolution date of an adverse event is missing day only, it will be set to the earliest of the last day of the month of occurrence of resolution, the day of withdrawal, study completion, or the day of the date of death, if withdrawal, study completion, or death occurred in that month.

- If the resolution date of an adverse event is missing both day and month, it will be set to the earliest of the date of withdrawal, study completion, December 31 of the year, or the day and month of the date of death, if the death occurred in that year.
- Completely missing resolution dates will not be imputed.

## Time

AE onset/resolution dates with missing times will be imputed as follows:

- A missing time of onset of an adverse event will be set as follows:
  - 00:00 as long as the onset date is after the treatment phase start date
- The missing time of resolution of an adverse event will be set to 23:59.

If a missing time is associated with a partial or missing date, the date will be imputed first prior to imputing the time.

## 3. INTERIM AND FINAL ANALYSIS

An interim analysis will be conducted. To control overall Type 1 error, O'Brien-Fleming boundary based on Lan-DeMets' alpha spending function will be used for analysis of primary endpoint based on the independent central radiology review (ICRR), and the null hypothesis for ORR of 14% will be rejected and efficacy will be declared if statistical significance is observed based on the O'Brien-Fleming boundary of Lan-DeMets' alpha spending function. In the interim analysis, futility analysis is also planned, the study will be concluded futile and will be stopped, if the count of responder is 1 or none. The stopping boundaries for efficacy and futility based on the O'Brien-Fleming boundary of Lan-DeMets' alpha spending function are displayed in [Table 1](#). Enrollment will not pause during interim analysis.

In this study, an interim analysis will be performed when 12 response evaluable participants (response evaluable population) who has been evaluated at least 24 weeks from the initiation of study intervention are observed. The interim analysis is performed based on the data from 12 response evaluable participants (response evaluable population) who has been evaluated at least 24 weeks from the initiation of study intervention or whose disease evaluation of primary endpoint has been determined within 24 weeks after the initiation of study intervention. If 13 or more response evaluable participants who meet the condition above are available at the timing of interim analysis, only the data of 12 response evaluable participants who are selected by date of obtaining informed consent will be used for primary analysis at the interim analysis. (If there are multiple response evaluable participants whose date of obtaining informed consent is the same, who are with earlier date of the first study intervention will be used. If informed consent date and first study intervention date are used and response evaluable participant is still not unique, who are with smaller number of study site number will be used. ie, Response evaluable participants are selected in order of the date of obtaining informed consent, the date of first study intervention and study site number from the participants who meet the condition above.) The analysis of primary endpoint using data including 13th or more response evaluable participants (in the same order of above) and thereafter will be used for supplemental analysis.

The final analysis will be performed when 24 response evaluable participants (response evaluable population) who has been evaluated at least 24 weeks from the initiation of study intervention are observed. The final analysis is performed based on the data from 24 response evaluable participants (response evaluable population) who has been evaluated at least 24 weeks from the initiation of study intervention or whose disease evaluation of primary endpoint has been determined within 24 weeks after the initiation of study intervention. If 25 or more response evaluable participants who meet the condition above are available at the timing of final analysis, only the data of 24 response evaluable participants who are selected by the date of obtaining informed consent will be used for primary analysis at the final analysis. (If there are multiple response evaluable participants whose date of obtaining informed consent is the same, as the same way of interim analysis, response evaluable participants are selected in order of the date of obtaining informed consent, the date of first study intervention and study site number from the participants who meet the condition above.) The analysis of primary endpoint using data including 25th or more response evaluable participants (in the same order of above) and thereafter will be used for supplemental analysis. The final supplemental analysis may be conducted at the end of the study.

As mentioned above, the fixed number (12 and 24) of response evaluable participants who meet the condition above are used in the analysis of primary endpoint at the interim and the final analysis for efficacy and futility determination, more detail for the selection rule of response evaluable participants who are analyzed in primary analysis of the IA and the FA is described in the Section 3.1, and more detail for efficacy analysis of primary endpoint and the analyses for other efficacy endpoints are described in the Section 5.

The sponsor will establish a data cutoff date for interim analyses. The sponsor will determine whether futility or efficacy will be declared based solely on the result of primary endpoint which based on the independent central radiology review (ICRR) and the efficacy and futility boundaries of Table 1.

At the interim analysis, only selected analyses listed in Table 2 will be conducted. At the final analysis, all analyses planned in this SAP will be performed.

**Table 1: Efficacy and Futility Boundaries Using Alpha Spending Function**

The timing of analysis (Number of Response evaluable Participants)	Maximum Number of Responders for Futility	Minimum Number of Responders for Efficacy	Cumulative Alpha Spent Based on Alpha Spending Function
12	1	7	0.15%
24	-	8	2.5%

The right most column in Table 1 shows cumulative alpha based on alpha spending function in this study.

**Table 2: Summary of Selected Analyses at the Interim Analysis**

	Analysis	Analysis Set
Subject Information	Summary of Demographics and Baseline Characteristics	Treated, Response evaluable
	Disposition Information	Treated, Response evaluable

	Analysis	Analysis Set
	Summary of Exposure and Dose Adjustment	Treated
	Summary of Prior SGC Related Therapy	Treated, Response evaluable
	Current General Medical History by System Organ Class (SOC) and Preferred Term (PT)	Treated
Efficacy	Summary of Overall Response Rate Including Supplemental Analysis with Expansion Data – ICRR/Investigator Judgement	Response evaluable
	Subgroup Analysis for Overall Response Rate Including Supplemental Analysis with Expansion Data – ICRR Judgement	Response evaluable
	Waterfall Plot and Swimlane Plot Including Supplemental Analysis with Expansion Data – ICRR Judgement	Response evaluable
	Summary of Disease Control Rate Including Supplemental Analysis with Expansion Data – ICRR Judgement	Response evaluable
	Summary of Clinical Benefit Rate Including Supplemental Analysis with Expansion Data – ICRR Judgement	Response evaluable
	Summary of Duration of Response Including Supplemental Analysis with Expansion Data – ICRR Judgement	Responders in Response evaluable
	Summary of Time to Response Including Supplemental Analysis with Expansion Data – ICRR Judgement	Responders in Response evaluable
	Summary of Overall Survival and Kaplan-Meier Plot	Treated
	Summary of Progress-Free Survival and Kaplan-Meier Plot – ICRR Judgement	Treated
Safety	Overall Summary of Treatment-emergent Adverse Events (TEAEs)	Treated
	TEAEs by SOC, PT, and Toxicity Grade	Treated
	Related TEAEs by SOC, PT, Toxicity Grade and Study Agent	Treated
	TEAEs of Special Interest by SOC, PT and Toxicity Grade	Treated
	Serious TEAEs by SOC, PT and Toxicity Grade	Treated
	Related Serious TEAEs by SOC, PT, Toxicity Grade and Study Agent	Treated
	TEAEs leading to Discontinuation of Study Agent by SOC, PT and Toxicity Grade	Treated
	Related TEAEs leading to Discontinuation of Study Agent by SOC, PT and Study Agent	Treated
	TEAEs Leading to Dose Reduction or Interruption of Apalutamide by SOC and PT	Treated
	TEAEs Leading to Dose Interruption or Delay of Goserelin by SOC and PT	Treated
	TEAEs Leading to Death by SOC and PT	Treated
	TEAEs of Toxicity Grade 3 or Greater by SOC and PT	Treated
	Related TEAEs of Toxicity Grade 3 or Greater by SOC, PT and Study Agent	Treated

### **3.1. Selection rule of response evaluable participants who are used in IA and FA**

In the primary analysis of interim and final analysis, 12 and 24 response evaluable participants (response evaluable population) who has been evaluated at least 24 weeks from the initiation of study intervention or whose disease evaluation of primary endpoint has been determined within 24 weeks after the initiation of study intervention are analyzed respectively. ie, The 12 and 24 response evaluable participants who meet the at least one condition listed below will be analyzed in the primary analysis of IA and FA respectively.

1. Who evaluated at least 24 weeks from the initiation of study intervention (has cycle 7 visit efficacy disease assessment).
2. Whose ICRR disease evaluation is confirmed as  $\geq$ PR within 24 weeks from the initiation of study intervention (disease evaluation of primary endpoint is determined at the first confirmed date of  $\geq$ PR)
3. Whose ICRR disease evaluation is PD within 24 weeks from the initiation of study intervention (disease evaluation of primary endpoint is determined at the first PD date of ICRR)
4. Who completed study participation (disease evaluation of primary endpoint is determined at death date, the date of withdrawal from consent, the last contact date if the participant is lost of follow up)
5. Who started subsequent therapy (disease evaluation of primary endpoint is determined at the date of subsequent therapy initiation)

If there are more than 12 or 24 response evaluable participants who meet the condition above at the timing of IA or FA, response evaluable participants are selected in order of the date of obtaining informed consent, the date of first study intervention and study site number from the participants who meet the condition above.

